This will be a cluster randomized control trial(C-RCT) conducted in Pune and Sangli district under field practice area of two medical colleges of Bharati Vidyapeeth University for a period of two years. The overall budget for the project is Rs. 11,449,580. The aim is to assess the efficacy of community based interventions in reducing incidence of pneumonia .To achieve 80% power and assuming intra-class coefficient of variation of 0.5, the study will randomly select and enrol 16 clusters with around 4800 children into intervention and comparison arm. The community based interventions in the form of behavioural change communication (BCC) activities under following domain will be implemented viz. child feeding practices, immunization, indoor air pollution, hand hygiene of mother at 4 occasions(after defecation, after cleaning child's bottom, before food preparation, before feeding the child), knowledge attitude and practices of mother about pneumonia, cough etiquettes. These interventions will be implemented by the project appointed field supervisors in the interventional clusters for mothers of under five children. These supervisors will be trained through project. Pneumonia surveillance will be conducted at fortnightly visits by ASHA/Anganwadi worker in both the arm for a period of one year. Incidence of pneumonia will be compared in both the arms. Quality will be assured by continuous monitoring of activities through sub-investigators. The progress of project will be reviewed in monthly meetings with partners. Assessment of efficacy of community based interventions in reduction of incidence pneumonia will done.

Protocol

1. Title of the research proposal project:

Pneumonia Research Initiative in Rural Areas and Urban Slums of Maharashtra

2. Problem statement:

Recent statistics indicates that in Maharashtra the fortnight period prevalence of ARI among children under 5 years of age is 8.5 % and 9.3% in urban and rural areas respectively (DLHS-4). Some children develop pneumonia which is responsible for 14% of total under five deaths (UNICEF 2012). Pneumonia is a leading cause of death among children under 5 years of age. One of the reasons for not achieving the Millennium Development Goal 4 (reduction in child mortality) is poor access to health facilities and paucity of trained human resources in primary health setups.

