2. Second round of BCC activities: This will be conducted for reinforcement of the information delivered in first round. It will be conducted again in small groups after 2 months of first round and completed in two months. In this round emphasis will be given on skills acquired and demonstration by participants.

Various BCC activities will be supervised by sub-investigators.

Training of ASHA/AWW:

Investigators will train AWW & ASHA from intervention arm to orient them about the objectives, importance of project and their role in the project for surveillance.

Contents of the training modules:

- a. Introductory contents pertaining to pneumonia: protocol specific training, IMNCI guidelines for ARI/Pneumonia, diagnosis and standard management of pneumonia, problem statement of ARI/Pneumonia in their area.
- b. Surveillance related training: Fortnightly surveillance, maintenance of diary
- c. Communication skills and conducting session for mothers.
 Investigators will train all AWW and ASHA from both the arms regarding surveillance. Duration of training for ASHA/AWW:One day.

ASHA/AWW/FS from intervention arm will be requested to share their mobile numbers with mothers so that in case of any need like of sickness of child mother can contact them. The importance of response to mothers call will be emphasized as it may ensure appropriate management of child's illness and prevent the mortality. Training about fortnightly surveillance will be imparted to them.

Information about available emergency services like help line 108,102 will be given and ASHA/AWW/FS will communicate their mobile numbers to mothers/expectant mothers and will appeal to contact on same whenever the child is sick.

Phase 4: Followup and continued Intervention (12 months)

Pneumonia surveillance: This will be done in intervention arm for a period of one year by AWW/ASHA in rural area and AWW in urban slums through fortnightly house to house visit and enquiring about signs and symptoms related to pneumonia in preceding fortnight. This will help to calculate the fortnight incidence of pneumonia. Fortnightly visits will be adequate to get incidence of pneumonia in addition to this the mobile numbers of ASHA will be shared to mothers so that in case of any need like sickness of child mother can contact them. This will help to record attacks of pneumonia if any between the two fortnight visits.

Following definitions from IMNCI Guidelines will be used:

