Pneumonia: child with cough or difficulty in breathing as having pneumonia.

severe pneumonia: If the symptoms are associated with lower chest wall in drawing or subcostal retraction,

Very severe pneumonia: If there is a danger sign such as central cyanosis, or severe respiratory distress, convulsion, inability to rouse the child or if the child is unable to drink.

Interval: An episode of pneumonia after 7 days of previous episode will be counted as a new episode.

If answer is yes then ASHA/AWW will enter the information in the diary maintained by her and submit information to site investigators(SI). They will confirm the pneumonia using WHO IMNCI protocol.

Appropriate management of child's illness will be ensured. This record will be submitted in fortnightly meeting (one will coincide with their monthly meeting) with FS and the same will be updated periodically. In addition, information about any death among under five children will be collected and the cause of death will be ascertained.

Continued intervention: Will be given by field supervisor (FS) through monthly house to house visits During her house to house visits in intervention arm FS will interact with all mothers and enquire about practicing the methods, skills steps learnt during intensive intervention. In case of unsatisfactory response FS will reinforce the knowledge and skills.

The sub investigator will supervise a pair of cluster from intervention and comparison arm and will do surprise home visit to cross check information collected by AWW/ASHA.

In comparison clusters ASHA/AWW will continue their role as per existing guidelines and collect information about pneumonia and deaths due to pneumonia through fortnightly house to house visits and submitted to FS fortnightly. And AWW and ASHA will continue to

promote all activities that are part of national programme (immunisation, optimal feeding practices) in control sites.

Midterm evaluation of the project will be done by third party at the end of three months of surveillance.

Detection and referral of pneumonia cases is a part of routine activity of ASHA/AWW workers so stopping of these duties is not advisable. And they will be closely monitored by field supervisors and sub investigators.

Standard care for ARI / Pneumonia will be provided to referred children through our own institutions and partner in public sector in two districts.

Phase 5: Data Analysis (2 months) and Final Report writing (1 month)

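### The protocol contradicts itself on whether case confirmation and between-visit reporting apply in both arms, so the primary outcome may be ascertained differently by arm.

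*Protocol*

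**What the plan says.** The summary at the head of the protocol states: "Pneumonia surveillance will be conducted at fortnightly visits by ASHA/Anganwadi worker in both the arm for a period of one year".

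Phase 4 (Followup and continued Intervention) opens differently: "Pneumonia surveillance: This will be done in intervention arm for a period of one year by AWW/ASHA in rural area", and by AWW in urban slums. The same block goes on to give the case definitions, the 7-day rule for a new episode and the handling of a positive answer: "If answer is yes then ASHA/AWW will enter the information in the diary maintained by her and submit information to site investigators(SI"). Of the site investigators it then says: "They will confirm the pneumonia using WHO IMNCI protocol". The block also has workers' mobile numbers given to mothers, so that attacks between two visits are recorded. Under Training of ASHA/AWW in Phase 3, the request to share numbers is addressed to workers and field supervisors of the intervention arm.

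Comparison clusters have a separate paragraph later in Phase 4: "In comparison clusters ASHA/AWW will continue their role as per existing guidelines and collect information about pneumonia and deaths due to pneumonia", to be done "through fortnightly house to house visits and submitted to FS fortnightly". It mentions no site investigator, no confirmation and no telephone route.

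Key Outcomes defines the primary outcome as the incidence of pneumonia, calculated and compared in both arms. It does not say whether a counted case is a reported or a confirmed one.

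**The concern.** The trial has one primary comparison, and it is valid only if a case is found and counted in the same way in both arms. Read literally, Phase 4 gives the intervention arm two steps that the comparison arm lacks. Confirmation removes reports that do not meet the definition. Telephone contact adds reports that a fortnightly visit might miss. Each changes the count in one arm for reasons unrelated to whether the programme prevents pneumonia.

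This is a field procedure, not an analysis detail that can be settled later. If comparison-arm reports are not confirmed when they arise, no analysis can restore that step. Because Key Outcomes does not say which cases count, nothing later in the protocol resolves the conflict.

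**Working it through.** **Step 1: the texts side by side**

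| Element | Summary | Phase 4 surveillance block | Phase 4 comparison-cluster paragraph |
|---|---|---|---|
| Arm named | both | intervention | comparison |
| Fortnightly home visits | yes | yes | yes |
| Record to field supervisor | not stated | yes, at the fortnightly meeting | yes, fortnightly |
| Submission to site investigator | not stated | yes | not stated |
| IMNCI confirmation | not stated | yes (the sentence itself names no arm) | not stated |
| Mobile numbers for between-visit episodes | not stated | yes | not stated |

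Submission to the field supervisor is common to both arms. The differences are the site-investigator step and the telephone route.

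**Step 2: model for the observed rate ratio**

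Let R be the true rate ratio, c the share of intervention-arm reports kept after confirmation, and e the proportional increase in intervention-arm reports from telephone contact. Suppose all comparison-arm reports count, and telephone reports are confirmed at the same share c. Then

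observed ratio = R × c × (1 + e).

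The protocol gives no value for c or e, so there is no plan figure to reproduce. Both are assumptions, shown as ranges.

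**Step 3: no true effect (R = 1), confirmation in one arm, e = 0**

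- c = 0.9: ratio 0.90, a spurious reduction of 10%
- c = 0.7: ratio 0.70, a spurious reduction of 30%
- c = 0.5: ratio 0.50, a spurious reduction of 50%, equal to the whole effect hypothesised in the protocol

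**Step 4: no true effect, with telephone reporting also in one arm**

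- c = 0.9, e = 0.25: 0.9 × 1.25 = 1.125
- c = 0.8, e = 0.25: 0.8 × 1.25 = 1.00
- c = 0.7, e = 0.5: 0.7 × 1.5 = 1.05
- c = 0.5, e = 0.5: 0.5 × 1.5 = 0.75

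The two biases cancel when e = 1/c − 1, that is at e = 0.11, 0.43 and 1.00 for c = 0.9, 0.7 and 0.5. Below that value the intervention looks better than it is; above it, worse.

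**Step 5: could a bias of this size reach significance?**

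Inputs from the sample-size section: comparison rate a = 0.30, cluster size m = 300, 8 clusters per arm, and between-cluster variation 0.5, read here as a coefficient of variation k. A two-sided 5% level is assumed because none is stated. With b = 0.30c and e = 0,

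SE² = {[a(1−a) + b(1−b)]/m + k²(a² + b²)} / (8 − 1).

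For c = 0.7, b = 0.21:

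- SE² = (0.00125 + 0.03353)/7 = 0.00497, so SE = 0.0705.
- z = 0.09/0.0705 = 1.28.
- The chance of a significant result is about 25%.

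The same calculation gives about 7% at c = 0.9 and 64% at c = 0.5. These are normal approximations and apply only when telephone capture adds nothing.

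**Step 6: after alignment**

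If both arms have the same c and e, these factors appear in numerator and denominator and cancel. The observed ratio is then R.

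**The case against.** The strongest reply is that this is loose drafting, and that both arms were always meant to be handled alike. Several parts of it stand.

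- The confirmation sentence names no arm. The case definitions and the 7-day rule sit in the same block, and it would be odd if they applied only to intervention clusters.
- Workers of both arms are trained in surveillance. A sub-investigator supervises a pair of clusters, one from each arm, with surprise home visits.
- One later sentence in the training text, on emergency services, has workers giving out their numbers without naming an arm.

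A reader might therefore infer too much: that the protocol deliberately compares confirmed cases with raw worker reports and will produce a false benefit. The documents do not support that. They contradict each other rather than fix such a plan, and comparison-arm reports do receive some oversight. The direction is also open, because telephone reporting, and teaching mothers the signs and prompt contact, would raise intervention-arm counts.

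Nor do the documents support a very low confirmed fraction. The broad definition, "Pneumonia: child with cough or difficulty in breathing as having pneumonia", is presented as coming from IMNCI, the same standard named for confirmation, and the sentence is too garbled to carry much weight.

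The reply does not remove the problem. The quality-assurance section has the supervisor cross-check 5% of study tools and the sub-investigator 2% of forms; neither is confirmation of each case. Staff who follow Phase 4 as written would confirm cases in one arm only. Two opposing biases of unknown size do not make a fair comparison.

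**Conclusion.** The concern holds as an unresolved contradiction in how the primary outcome is ascertained. The summary and Phase 4 disagree on where surveillance takes place, and the confirmation and between-visit steps are written only into intervention-arm text.

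Followed literally, the observed ratio is multiplied by c(1+e). Over the assumed values in Steps 3 and 4, a null programme would show a ratio anywhere from 0.50 to 1.125. This rests on assumed c and e, and on counting every comparison-arm report. A false benefit as large as the hypothesised 50% needs c = 0.5 with no extra telephone capture. It is possible, but nothing in the protocol shows it is likely. That the texts must be reconciled before surveillance starts is certain; the size and sign of any bias are not.

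**What to change.** 1. Reword the opening of the Phase 4 surveillance paragraph to say that surveillance is done in both arms.
2. Apply one pathway everywhere: the same fortnightly questions, diary, between-visit reporting route, submission to the site investigator and confirmation step. Bring the comparison-cluster paragraph and the mobile-number text under Training of ASHA/AWW into line.
3. State under Key Outcomes that the primary outcome counts site-investigator-confirmed episodes in both arms. Where practicable, whoever confirms should not know the cluster's allocation, since mothers in intervention clusters are taught to recognise and report illness.
4. If confirmation cannot cover both arms, count worker-reported episodes from the fortnightly visits in both arms, leave out telephone-only reports, and state that this outcome is less specific.

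The cost is wording plus site-investigator time in comparison clusters. If the planning rate of 0.30 is taken as the confirmed rate, 8 clusters × 300 children × 0.30 gives about 720 confirmed episodes in a year. That means 720/c reports to assess: 800 at c = 0.9 and 1,440 at c = 0.5. The summary's commitment to surveillance in both arms arguably implies this work already. The fallback saves that work but gives up specificity in the primary outcome.

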Aim: To assess the efficacy of community based interventions in reducing incidence of pneumonia.

Objectives:

To compare the incidence of pneumonia among under five year children from intervention and comparison clusters after selected community based interventions.

[figure not shown]
5. Study Protocol/Detailed research plan:

Study design: A cluster randomized trial in Pune and Sangli district stratified by urban slums and villages.

Study area: Bharati Vidyapeeth University is a multidisciplinary and multi centric university having two medical colleges in Pune and Sangli districts of Maharashtra state of India. This study will be carried out in 4 sites under the urban and rural field practice area of these two medical colleges. Each site is having 9-16 clusters of slums/ villages.

Number of clusters and sample size calculation:

Figure-1

A review article indicates that incidence of childhood pneumonia is 0.2 to 0.5 per child per year (Ghimire M. et al 2012). This is equivalent to 20% to 50% of incidence of pneumonia. For sample size calculations we have assumed the incidence rate at 30%. Community based intervention is expected to reduce the incidence rate by 50%. The curve required for various powers and number of clusters is shown in figure-1. Sample size assumptions and estimations are reviewed by a statistician.

To achieve 80% power and assuming intra-class coefficient of variation to be 0.5, the study will need to enrol minimum 15 clusters of average 300 size. However we have decided to include 16 clusters.

Thus the total number of children under 5 years to be enrolled in the study will be about 4800.

The field practice areas of both medical colleges together have 47 available clusters; 16 clusters will be selected randomly and allocated to intervention arm and comparison arm by randomization. Thus there will be 8 clusters in intervention arm and equal number in comparison arm.

All under five year children residing in the selected clusters and their mothers (including expectant mothers) will constitute study subjects. The process of inclusion of subjects (mothers and children) will continue throughout the study period. Those children who complete five years of age in the project period will be excluded. However, these children will be considered while calculating denominator of children-months.

Study tools: Following tools will be developed and used for data collection and intervention

- 1. Trainer's modules

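### The only written definition of base-tier pneumonia has no sign separating it from other ARI, and the protocol does not say whether reported or confirmed cases are counted, or that both arms are confirmed alike

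*Protocol*

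**What the plan says.** The protocol's Phase 4 section introduces its case definitions with "Following definitions from IMNCI Guidelines will be used". The first reads "Pneumonia: child with cough or difficulty in breathing as having pneumonia". The next tier adds signs to the same symptoms: "severe pneumonia: If the symptoms are associated with lower chest wall in drawing or subcostal retraction". The base tier is therefore the symptoms alone.

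A positive answer goes into the worker's diary and on to the site investigators: "They will confirm the pneumonia using WHO IMNCI protocol". The criterion they apply is not written out. For comparison clusters the same section says that workers "collect information about pneumonia and deaths due to pneumonia through fortnightly house to house visits and submitted to FS fortnightly", and it mentions no site-investigator confirmation there.

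The Problem statement gives the background frequency of ARI: "the fortnight period prevalence of ARI among children under 5 years of age is 8.5 % and 9.3% in urban and rural areas respectively". It then says that some children develop pneumonia. The sample size section cites a pneumonia incidence of 0.2 to 0.5 per child per year and continues "For sample size calculations we have assumed the incidence rate at 30" per cent, with an expected halving. Key Outcomes names the incidence of pneumonia in both arms as primary and does not say which cases count.

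**The concern.** The primary outcome needs a rule that tells pneumonia from a cough or cold. The only rule in print does not do so, although the rest of the protocol treats pneumonia as a subset of ARI. If the printed rule were used for counting, the trial would mostly measure cough. The event rate would not match the planning rate, and a real effect on pneumonia would be obscured by events that the intervention may not change as much.

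The arms may also be counted differently. If confirmed cases in one arm were compared with worker reports in the other, the gap between the two kinds of case could look like a treatment effect.

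This cannot be left to the analysis stage. Events are recorded prospectively by field workers, and a sign that nobody recorded cannot be recovered later.

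**Working it through.** The protocol derives no event rate from its case definition, so there is no such figure to reproduce. The planning rate of 0.30 is chosen from within the cited 0.2 to 0.5. The check asks what rate the written wording would give on the protocol's own ARI figures.

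**Inputs**
- ARI fortnight prevalence: 8.5% urban, 9.3% rural (Problem statement).
- Planned pneumonia incidence: 0.30 per child-year, cited range 0.2 to 0.5 (sample size section).
- Planned effect: 50% reduction (sample size section).
- Assumption: survey ARI is equivalent to the written symptoms. The survey's ARI definition is not in the protocol.
- Assumption: carry-over of episodes between fortnights. The protocol gives no figure.

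**Upper end, no carry-over.** Rate = 26 × fortnight prevalence.
- Urban: 26 × 0.085 = 2.21 per child-year; 2.21 / 0.30 = 7.4 fold.
- Rural: 26 × 0.093 = 2.42 per child-year; 2.42 / 0.30 = 8.1 fold.

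**Lower end, half carried over.**
- Urban: 2.21 / 2 = 1.11; 1.11 / 0.30 = 3.7 fold.
- Rural: 2.42 / 2 = 1.21; 1.21 / 0.30 = 4.0 fold.

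**Same question by episode duration.** Rate = prevalence × 365 / (14 + d), where d is an assumed mean duration in days.

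| d (days) | Rate per child-year, urban to rural | Multiple of 0.30 |
|---|---|---|
| 3 | 1.83 to 2.00 | 6.1 to 6.7 |
| 7 | 1.48 to 1.62 | 4.9 to 5.4 |
| 14 | 1.11 to 1.21 | 3.7 to 4.0 |

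The 4-fold end thus corresponds to a mean duration of about 14 days.

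**Across the cited pneumonia range.** Smallest multiple: 1.11 / 0.5 = 2.2. Largest: 2.42 / 0.2 = 12.1.

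**Dilution, if only pneumonia is halved and other ARI is unchanged.** Observed reduction = (0.5 × pneumonia rate) / counted rate.
- At 0.30: 0.15 / 2.42 = 6% to 0.15 / 1.11 = 14%, a rate ratio of about 0.94 to 0.86 against the planned 0.50.
- Across 0.2 to 0.5: 0.10 / 2.42 = 4% to 0.25 / 1.11 = 23%.

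**Ascertainment by arm.** In the intervention arm, Phase 4 describes worker visit, diary, site investigator and confirmation. In comparison clusters it describes worker visit and submission to the field supervisor. Sub-investigators do cross-check visits in paired clusters from both arms, but the quality assurance section sets this at 2% of forms, which is not case-by-case confirmation.

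**The case against.** The strongest reply is that the base-tier sentence looks defective rather than intended. It is ungrammatical and seems to have lost words, it is offered as an IMNCI definition, workers and supervisors are trained on IMNCI, and site investigators confirm by the IMNCI protocol. On that reading coughs are screened out before anything is counted. This carries weight. A reader might infer that the endpoint will certainly be swamped by coughs, and the protocol does not support that: the excess reaches the endpoint only if unconfirmed reports are counted or if confirmation uses the same bare wording. What remains is that neither possibility is excluded, and the only criterion in print is the non-specific one.

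A reader might also infer that the 4-to-8-fold range comes wholly from the protocol's figures. Only the upper end is 26 times the printed prevalence, and even that is an upper bound which equates survey ARI with the written symptoms. The lower end rests on an assumed carry-over.

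The dilution figures likewise assume no effect on other ARI. The intervention includes hand hygiene, cough etiquette and indoor air pollution, and the protocol expects wider benefits, so other ARI might fall too. The dilution would then be smaller, but the result would still be about ARI.

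Finally, it is tempting to say that comparison-arm cases will not be confirmed. The protocol does not say so. Its opening summary has surveillance in both arms, and all workers are trained for it. The text is silent on confirmation in comparison clusters, which leaves the point open.

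**Conclusion.** The concern holds as an internal inconsistency in the definition of the primary outcome. The written base-tier definition does not separate pneumonia from other ARI, and it does not fit the Problem statement or the 0.30 planning rate. The protocol leaves open whether reported or confirmed cases are counted and whether both arms are confirmed alike.

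The size is conditional. Counting on the written wording without a more specific confirmation could give roughly 4 to 8 times the planned rate, or about 2 to 12 times across the cited range, with heavy dilution of an effect confined to pneumonia. Confidence in the defect is high. Confidence in the multiple is only moderate, because it rests on the ARI equivalence and the carry-over assumption. The matter should be settled before surveillance starts, since it concerns the sole primary outcome.

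**What to change.** 1. Make cough or breathing difficulty the screening trigger only.
2. Reconcile the written definition with the cited IMNCI protocol by writing out the criterion that distinguishes pneumonia from other ARI.
3. Name the episode meeting that criterion as the primary outcome, and say whether it must be confirmed by a site investigator.
4. State one counting and confirmation rule for both arms.
5. Report trigger-positive episodes separately as ARI.

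If confirmation cannot be done in both arms, use the same worker-recorded specific criterion in both arms for the primary comparison.

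The cost is a wording change and a change to the diary and confirmation form, plus confirmation work in comparison clusters if it is not already intended there. That work may not be small. With 8 clusters of about 300 children (2,400), the illustrative rates imply 1.105 × 2,400 = about 2,650 to 2.418 × 2,400 = about 5,800 trigger-positive reports over the surveillance year. Some reports will be up to a fortnight old when they reach the investigator, so the form should record the distinguishing criterion at the worker's visit.

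### The 7-day new-episode rule has no stated start point and no symptom-free requirement, so one illness that spans a fortnightly visit can be counted more than once in the primary outcome

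*Protocol*

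**What the plan says.** The rule stands among the definitions in Protocol section 5, Phase 4, under Interval: "An episode of pneumonia after 7 days of previous episode will be counted as a new episode". The reports it acts on come from surveillance in the same phase. In the intervention arm this is a "fortnightly house to house visit and enquiring about signs and symptoms related to pneumonia in preceding fortnight". In comparison clusters the workers "collect information about pneumonia and deaths due to pneumonia through fortnightly house to house visits". A positive answer goes into the worker's diary and then to the site investigators, of whom the protocol says: "They will confirm the pneumonia using WHO IMNCI protocol".

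The symptom definition is broad as worded: "Pneumonia: child with cough or difficulty in breathing as having pneumonia".

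Reports can also arrive by telephone. Under the training of ASHA/AWW, "ASHA/AWW/FS from intervention arm will be requested to share their mobile numbers with mothers"; Phase 4 gives the purpose: "This will help to record attacks of pneumonia if any between the two fortnight visits".

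The primary outcome (Key Outcomes) is the incidence of pneumonia compared between arms. The sample size section refers to a denominator in child-months, so with the Interval rule the outcome reads as a rate of episodes.

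**The concern.** The enquiry looks back over a fortnight. A child who is ill on both sides of a visit gives a truthful yes at that visit and at the next one. Whether the second yes is a new episode depends on where the 7 days start, and three readings are open: onset, last symptomatic day, or date of report. The text chooses none and does not say that a continuing illness stays one episode.

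The count of episodes is the numerator of the primary outcome. If workers or sites apply different readings, the counted rates differ with no difference in disease. A later analysis cannot repair this unless the first and last symptomatic days were collected, so it has to be settled before surveillance starts.

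**Working it through.** **Inputs.** From the protocol: 14 days between visits; recall of the preceding fortnight (stated for the intervention arm, assumed the same in the comparison arm); the 7-day rule; planning incidence 0.30 per child-year. Assumed, because the protocol gives no illness duration: one continuous illness of D days, D from 3 to 14, with onset equally likely on any day of the 14-day cycle, and every yes entering the count. The protocol gives no figure for counts per illness, so there is none to reproduce first.

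**(a) Seven days from the date of report.** The expected number of visits falling within the illness is D/14, and each adds one further yes. Consecutive reports are 14 days apart, which exceeds 7, so each counts as new.

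Counted episodes per illness = 1 + D/14.
- D = 3: 1 + 3/14 = 1.21
- D = 5: 1 + 5/14 = 1.36
- D = 7: 1 + 7/14 = 1.50
- D = 10: 1 + 10/14 = 1.71
- D = 14: 1 + 14/14 = 2.00

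The formula is linear in D, so under this reading only the mean duration matters.

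**(b) Seven days from onset.** Up to D = 7 the count is 1.00. Beyond that it depends on a further convention.
- Strict: the second report counts only if its recall window opens more than 7 days after onset. Count = 1 + (D − 7)/14, which is 1 + 3/14 = 1.21 at D = 10.
- Lenient: any symptom after day 7 makes the second yes a new episode. Count = 1 + D/14, which is 1.71 at D = 10.

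**(c) Seven days from the last symptomatic day, with dates recorded.** The count is 1.00 at every D from 3 to 14.

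A simulation of 400,000 illnesses per setting agrees with these formulas to within 0.003, apart from a rounding artefact in the lenient version at exactly D = 7.

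**Effect on the rate.** A true 0.30 per child-year would be counted under (a) as 0.30 × 1.36 = 0.41 (D = 5), 0.30 × 1.50 = 0.45 (D = 7) or 0.30 × 1.71 = 0.51 (D = 10), and under (c) as 0.30.

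**Effect on the comparison.** With the same distribution of durations and the same reporting channels in both arms, the inflation factor cancels and the rate ratio is unchanged under every reading. The absolute difference between arms is multiplied by the factor.

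If durations differed and true incidence did not, the counted rate ratio (intervention to comparison) would be:

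| Assumed days, comparison vs intervention | (a) | (b) strict | (c) |
|---|---|---|---|
| 7 vs 5 | 19/21 = 0.90 | 1.00 | 1.00 |
| 10 vs 8 | 22/24 = 0.92 | 15/17 = 0.88 | 1.00 |
| 14 vs 10 | 24/28 = 0.86 | 17/21 = 0.81 | 1.00 |

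**Phone reports act the other way.** Take an illness contained in one fortnight, phoned in at a random point and recalled at the next visit. Under (a) the visit falls more than 7 days after the call with probability 7/14 = 0.50, so the expected count is 1.50 instead of 1.00. If a share p of such illnesses is phoned in, the factor is 1 + 0.5p. Where only the intervention arm has this channel, its counted rate rises.

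**The case against.** **The plain reading is harmless.** The rule speaks of an episode following a previous episode, and a continuing illness is not a second episode. Report dates are not mentioned in it. This has force: reading (c) is natural and gives 1.00. But the text does not state it, and field workers will apply the rule to fortnightly yes/no answers, where reading (a) is the easiest to follow.

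**Investigators confirm each report.** This could remove some repeat reports. If only a quarter to a half of them were confirmed (an assumption), the count under (a) would be 1 + 0.25 × 7/14 = 1.13 to 1 + 0.50 × 7/14 = 1.25 at 7 days, and 1.18 to 1.36 at 10 days. The step reduces the problem without resolving it. It confirms a diagnosis; no rule is given for a child already confirmed a fortnight before, and a child still coughing meets the symptom definition as worded.

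**The diary may hold the dates.** The tool is still to be developed and its content is not shown, so it cannot be said that dates are missing. The point is that the rule needs them and does not ask for them.

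**Two stronger readings are tempting and not supported.** A reader might infer that 7 days being shorter than the 14-day visit interval is itself the fault. It is not: under (c) both figures stay as they are and the double count disappears. A reader might also infer that the rule builds in a false benefit, because care-seeking education in the intervention arm could shorten illness. The documents give no durations, overall or by arm, and phone reporting pushes the other way.

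**Conclusion.** The point holds as a defect in the counting rule. The rule has no start point and no symptom-free requirement, and the protocol does not say how two reports of one illness are joined. For an assumed 10-day illness the permitted readings run from 1.00 to 1.71 counted episodes, and for a 7-day illness from 1.00 to 1.50. These figures rest on assumed durations, uniform onset and every report being counted; confirmation would lower them.

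The established consequence is possible inflation of incidence in both arms, and rates that depend on how each worker or site reads the rule. Bias in the rate ratio is possible, because care-seeking education is given in the intervention arm and the request to share phone numbers is addressed to that arm's workers (a following sentence on sharing numbers names no arm). Neither its presence nor its direction is shown. The ratios of 0.81 to 0.92 above illustrate one direction under assumed differences in duration and are not an estimate for this trial.

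**What to change.** Reword the Interval definition along these lines: a new episode is counted only after at least 7 consecutive symptom-free days since the last symptomatic day of the previous episode. Name the symptoms that define a symptomatic day. Have the diary record the first and last symptomatic day of each illness in both arms. Apply one joining rule to visit and phone reports in both arms, and carry an illness still present at a visit forward as the same episode.

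The existing 7 days and the fortnightly visits stay as they are. This changes counting only and does not touch the care of the child. The cost is one sentence, two diary fields and a short addition to the surveillance training. The counted rate will be somewhat lower, partly because two distinct illnesses less than 7 symptom-free days apart will be merged.
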